4 STUDY DESIGN

4.1 OVERALL DESIGN

We hypothesized that computerized cognitive training (CCT), through engaging the task-control network and increasing cognitive control capacity, may augment the CBT response. In this study, eighteen clinically anxious children ages 7 to 17 will be recruited and assigned to CBT+CCT for up to 12 weeks; thirty-six age- and gender-matched anxious children will be recruited and assigned to CBT only for up to 12 weeks. Before and after therapy, all participants may complete structured clinical assessment of anxiety, a computerized evaluation of cognitive control capacity (e.g., NIH Toolbox; Zelazo, Anderson, Richler, Wallner-Allen, and Beaumont, 2013) and MRI scanning during a cognitive interference task and resting-state to assess brain activation and functional connectivity in the TCN. However, at P.I. discretion, participants may not be required to complete an fMRI. Participants may also complete structured clinical assessment of anxiety, computerized evaluation of cognitive control capacity, and MRI scanning during therapy.

This study will be incorporated into an ongoing fMRI study (HUM00118950, PI [name]) investigating dimensional brain-behavioral predictors of CBT outcomes in pediatric anxiety. In the parent R01 (HUM00118950), 210 youths (7-17 years) with impairing anxiety are being recruited and randomized 2:1 to receive 12-week CBT or a non-active control therapy, “relaxation and mentorship therapy” (RMT);

multilevel data including fMRI, DTI and clinical measures are collected before and after treatment. As part of the parent study, RMT completers are offered study CBT (at no cost), without additional scanning.

Study activities that may be completed remotely (i.e., Millisecond behavioral assessment, clinical measures and assessments, CCT, and CBT through the parent study) will be conducted via an encrypted HIPAA-compliant video conferencing platform (e.g., BlueJeans, Zoom), phone call, and/or Millisecond/Qualtrics links. It will be standard practice to conduct as many procedures remotely as possible to better protect subject(s)/parent(s) and staff against the risk of COVID-19. However, when remote visits are not possible (e.g., NIH toolbox behavioral assessments, fMRI), in-person visits will be allowed and the study will follow all U-M safety guidelines for entering and being in U-M buildings (e.g., COVID screenings, PPE, social distancing, etc.).

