Eighteen RMT subjects in the parent study will be recruited to our CBT+CCT group, and thirty-six age- and gender-matched CBT subjects in the parent study will be recruited to our CBT control group. The proposed study may add:

- 1) For all fifty-four subjects recruited from parent study:
 - a. NIH Toolbox and/or Millisecond behavioral assessment before and after the CBT course of therapy as well as once before the RMT course of treatment and once at about 3 weeks of CBT and another time if completing the fMRI following 4 weeks of at home CCT for the CBT+CCT group
 - b. BRIEF2 questionnaire before, after, and at about week 3 of the CBT course of treatment, as well as once before the RMT course of treatment and at the fMRI following 4 weeks of at home CCT for the CBT+CCT group
 - c. Clinical assessment of anxiety at week 3 of CBT treatment.
- 2) For patients originally randomized to RMT in the parent study who wish to enroll in the current study during their Optional CBT participation:
 - a. augmentation of the CBT offered by the parent R01 study with CCT games delivered prior to each CBT session (CBT+CCT) along with a brief survey (the Self-Assessment Manikin) they may be asked to complete before and after CCT
 - b. fMRI following 4 weeks of at home CCT, and fMRI following CBT+CCT completion
 - c. Clinical measures and assessments before and throughout the course of CBT treatment
 - d. at home CCT (~30 min/day), 5x per week, for up to 4 weeks, for up to two weeks before starting CBT and for up to 4 weeks after starting CBT, along with a brief survey (the Self-Assessment Manikin) they may complete before and after CCT

Data analyses will compare pre- and post-CBT data from the parent study with pre- and post-CBT+CCT data collected for the proposed study. These data will include NIH Toolbox and/or Millisecond measures of behavioral capacity for cognitive control; multi-modal assessment of TCN with fMRI, resting state and DTI; and, detailed assessment of anxiety symptoms using both clinician-interview and self-report. Pre- to post-therapy change in anxiety severity (clinician-measured) will serve as the primary outcome variable; regression analyses will be used to test for associations of anxiety change with changes in brain-behavioral indices of cognitive control following CBT compared to CBT+CCT. To increase clinical relevance of study results, analyses will also consider responder status, a common end point for clinical trials.

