4.3 JUSTIFICATION FOR INTERVENTION

The CBT intervention will consist of up to 12 weekly 60 minute sessions of the manualized therapy, adapted from the Coping Cat program, for the treatment of pediatric anxiety disorders. The CBT+CCT intervention will consist of ~30 minutes of CCT games prior to each CBT session, to engage cognitive control capacity prior to receipt of CBT. They may also receive up to 4 weeks of at home CCT to complete for up to two weeks before starting CBT and up to 4 weeks after starting CBT (~30 minutes per session). If assigned, this may be done at home 5 days per week. The CCT games will be designed to target focused attention, response inhibition, working memory and multiple simultaneous attention to constitute a general executive function training, and activate neural systems associated with executive function/cognitive control. Difficulty of the games will be titrated individually and by session to avoid boredom and progressively activate the functional systems underlying cognitive control, which we hypothesize will optimize participant's ability to engage in, and thus benefit from, in the CBT intervention. For both groups, participants will have to complete at least 8 intervention sessions.

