5.1 INCLUSION CRITERIA

In order to be eligible to participate in this study, an individual must meet the following criteria:

1. Parent or guardian willing to give informed consent, and children willing to give informed assent to participate in the study.
2. Must be actively enrolled and maintain eligibility in HUM00118950 to participate in the study.

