Participants will receive payments for the initial assessment through the parent study. For the current protocol, they will receive \$10 for each behavioral NIH toolbox and/or Millisecond assessment and BRIEF2 questionnaire before and after treatment as well as \$10 each for the NIH toolbox and/or Millisecond assessment and BRIEF2 completed before the RMT course of treatment, and around week 3 of CBT for CBT+CCT group as well as when completing the fMRI after completing 4 weeks of at home CCT. Participants in the CBT-only group will receive \$10 for the clinical assessment of anxiety and BRIEF2 they may complete at week 3 of CBT. Participants in the CBT+CCT group will receive \$50 per fMRI scan (i.e., up to 3 scans - 1 before, 1 during, and 1 after CBT+CCT may be completed if the subject has not participated in the parent study; up to 2 scans may be completed if the subject has participated in the parent study and already received a pre-CBT+CCT scan). Participants in CBT+CCT group will also receive \$15 for each CBT+CCT session (up to 12 sessions), \$10 for each week of at home CCT training they may complete for two weeks before beginning CBT and during the first 4 weeks of CBT, if they complete at least 4 of the 5 daily trainings. If it is requested for a participant to come back for additional interviews or additional practice sessions in the scanner, we will offer the participant \$15 for these visits as well. Additional \$50 payment(s) will be provided if they are asked to come in again due to any possible technical difficulties with the MRI scanner (but not for repeated scans where participants choose to abort scan and try again at a later date). The parent/guardian will receive the incentive. Payment for all participants will be made in a single payment at the completion of their participation in the study.

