6 STUDY INTERVENTION(S) OR EXPERIMENTAL MANIPULATION(S)

6.1 STUDY INTERVENTION(S) OR EXPERIMENTAL MANIPULATION(S) ADMINISTRATION

6.1.1 STUDY INTERVENTION OR EXPERIMENTAL MANIPULATION DESCRIPTION

Cognitive behavioral therapy: The CBT intervention is administered per the protocol of the parent study. It will consist of up to 12 weekly 60-minute sessions of the Coping Cat (ages 7-13) or Cat Project (ages 14-17) manualized programs that have demonstrated efficacy for the treatment of pediatric anxiety disorders (Kendall and Hektke, 2006; Beidas, Benjamin, Puleo, Edmunds and Kendall, 2010). Session content includes: building rapport, identifying anxious feelings/somatic responses and relaxation skills (Sessions 1-2); identifying and challenging anxious thoughts, problem-solving, and self-evaluation/reward (i.e., cognitive restructuring, Sessions 3-5); and, progressive exposure to anxiety provoking situations (sessions 6-12). Parenting content is incorporated into two sessions prior to the initiation of cognitive restructuring and exposure. On some occasions, it may not be clinically appropriate to include a parent in the sessions. This will be determined on an as-needed basis through clinical consensus meeting. Recent research shows that cognitive restructuring and exposure (but not relaxation training, RT) are the “active ingredients” of Coping Cat CBT. Thus, the Cat protocols have been adjusted for the current trial with RT condensed into 2 sessions rather than being delivered over 3-4 sessions as in CAMS). This will maintain fidelity to Coping Cat content, while reducing the increased likelihood of attrition associated with longer treatment protocols. Delivery of CBT intervention over the course of up to 12 (rather than 16) sessions is intended to a) maintain fidelity to Coping Cat content and closely mimic its delivery in CAMS (outcomes assessed at week 12) and b) minimize boredom and the potential effect on anxiety that could be associated with a longer duration control treatment.

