8.2 SAFETY ASSESSMENTS

- **fMRI Safety Screen form** in order to ensure that there are no contraindications for fMRI. This form is provided by the fMRI lab and is not included within study documentation. The most current version of this screening form will be used at all times to ensure the safety of participants undergoing fMRI.
- **Columbia Suicide Severity Rating Scale**, present/lifetime version (Posner, Oquendo et al. 2007). A clinician-rated scale assessing suicidal ideation and behavior.
- **Pediatric Anxiety Rating Scale (PARS)**. A clinician-administered assessment to rate the severity of anxiety symptoms associated with common DSM-V anxiety disorders (social phobia, separation anxiety disorder, and generalized anxiety disorder) in children. Total scores on this scale range from 0 to 30, with scores above 13 indicating clinically meaningful anxiety. Approximately 20–30 minutes. Symptom worsening: > 25% increased PARS score (referenced to baseline) for more than 2 assessments in 1 week

Any safety-related assessments (C-SSRS administered through the parent study, fMRI screening) or primary outcome measure (PARS– independent assessor may administer at weeks 0, 1, 3, 6, 9, and 12; missed week 9 will not be reported as a deviation) that are missed for a study visit/week of therapy a participant completed will be reported to the IRB as a protocol deviation. For the independent assessments, we will accept a window of \pm 1 week. For CBT+CCT group, the 3-week, 6-week, and 9-week PARS assessments are completed under this protocol only, and a PARS assessment may be completed under this protocol prior to beginning at-home CCT treatment if there have been more than about 6 weeks since the RMT week 12 PARS. For the CBT-only group, the 3-week PARS assessment is completed under this protocol only. However, for the other assessments, missing or late assessments will not be reported as protocol deviations unless they constitute > 10% of the total assessments. In order to accommodate inevitable scheduling conflicts, holidays, etc., participants will be allowed to miss up to 4 sessions of therapy, and the sessions must be completed within 16 weeks. These allowances should affect neither the scientific integrity nor the safety monitoring provisions of the protocol.

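### CCT is given only to children who have already completed RMT and opted into CBT as a second treatment, so the planned group tests cannot attribute a difference to CCT

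*Combined protocol and SAP*

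**What the plan says.** Section 4.1 describes a parent trial in which "210 youths (7-17 years) with impairing anxiety are being recruited and randomized 2:1 to receive 12-week CBT or a non-active control therapy" (RMT, a relaxation and mentorship therapy). Children who complete RMT are then offered CBT in the parent study, without further scans. The present study draws on both arms: "Eighteen RMT subjects in the parent study will be recruited to our CBT+CCT group, and thirty-six age- and gender-matched CBT subjects" are recruited as controls. CCT is added during the optional CBT of children first randomised to RMT. Section 6.3 repeats this allocation and says that the pilot is not randomised. Section 5.1 closes other routes of entry: "Must be actively enrolled and maintain eligibility in HUM00118950 to participate in the study". Section 8.2 confirms a full RMT course before CBT+CCT, since the PARS may be repeated "if there have been more than about 6 weeks since the RMT week 12 PARS".

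Sections 9.3.2 and 9.3.3 compare the two groups by 2x2 repeated-measures ANOVA (pre/post by group) and, for responders, by chi-square test. Neither has a term for treatment history. Section 4.2 says that the comparison is meant to show whether CCT augments CBT. Section 9.2 says that the study will supply effect sizes for an R01 or R61/R33 application.

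One clause does not fit. The payment text in Section 5.5 budgets three scans, "1 before, 1 during, and 1 after CBT+CCT may be completed if the subject has not participated in the parent study", which conflicts with the Section 5.1 criterion.

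**The concern.** Aims 1 to 3 attribute any additional change in the CBT+CCT group to CCT. That group also differs from the control group in its whole route into CBT: a completed course of another therapy, a decision to continue, and CBT given second. If any of these alters how a child changes during CBT, the group-by-time term absorbs it. A reader of the pilot, or of the grant application built on it, would then take the combined quantity for the effect of CCT. Section 6.3 discloses the lack of randomisation, but the plan nowhere says that its contrast cannot isolate CCT. Matching on age and gender may suggest that the groups are otherwise alike.

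**Working it through.** **1. The plan's own sample figures.** Section 5 gives therapy retention of 96.2% and an fMRI motion rate of 89%, and expects 32 CBT and 14 CBT+CCT children with usable data. The product gives 36 x 0.962 x 0.89 = 30.8 and 18 x 0.962 x 0.89 = 15.4. Both lie within two children of the stated figures, so 32 and 14 are used below.

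**2. What coincides exactly with CCT** (Sections 4.1, 5.1, 6.3).

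| Factor | CBT+CCT (18) | CBT-only (36) |
|---|---|---|
| CCT | all | none |
| Completed RMT | all | none |
| Selected as RMT completer choosing optional CBT | all | none |
| CBT as second study treatment | all | none |

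CBT-only children also consent to this protocol, but none had to finish another treatment first and then choose CBT.

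**3. Rank of the design.** With columns for intercept, CCT and prior RMT, the last two are identical, so the rank is 2 of 3. Adding age and sex gives rank 4 of 5. In long format, with intercept, time, and a main effect and a time interaction for each of CCT and prior RMT, the rank is 4 of 6. The time-by-CCT and time-by-RMT columns are the same. The same holds for the other two history factors in the table. More children recruited under the same rules would not change this.

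**4. What the interaction estimates.** Let mean change in the CBT group be *m*, and in the CBT+CCT group *m* + *c* + *h*. Here *c* is the CCT effect and *h* is everything that the route into CBT contributes to change. The group-by-time contrast is (*m* + *c* + *h*) - *m* = *c* + *h*. The data fix only the sum.

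**5. Illustration of consequence.** Set *c* = 0 and let *h* = *d* SD of the change score. The values of *d* are assumptions; the documents give none. The two-sided 5% test is a noncentral t with noncentrality *d* / sqrt(1/n1 + 1/n2). For 32 v 14, sqrt(1/32 + 1/14) = 0.320, with 44 df. For 36 v 18, sqrt(1/36 + 1/18) = 0.289, with 52 df.

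| *d* | 32 v 14 | 36 v 18 |
|---|---|---|
| 0 | 5% | 5% |
| 0.2 | 9.4% | 10.4% |
| 0.3 | 15.0% | 17.5% |
| 0.5 | 33.3% | 39.8% |

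Voxelwise fMRI tests use other thresholds (Section 9.3.1), so these rates apply to single-measure tests at the general 5% level.

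**6. What would break the aliasing.** Adding any child with prior RMT and CBT but no CCT raises the rank in step 3 from 2 to 3 of 3, so CCT and prior RMT become separable in an additive model. Section 6.3 names such a group, OPT CBT, when it discusses therapist blinding. No planned analysis uses it.

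**The case against.** The strongest reply is that RMT is a designated non-active control (Section 4.1) and that Section 6.1.1 says relaxation training is not an active ingredient of CBT. In addition, each group is measured from its own pre-CBT baseline, and the scan and PARS may be refreshed after about six weeks (Sections 8.1.3, 8.2). Nearly all RMT participants go on to CBT (Section 5), and both groups come from one randomised trial stratified on age and gender. The study is an openly non-randomised pilot without a power analysis.

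Much of this stands as mitigation, and it may mean that *h* is small. None of it shows that *h* is zero:

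- The non-active label describes RMT's role as a control. Section 6.1.1 itself allows that a control treatment could affect anxiety, and it keeps some relaxation content in the first CBT sessions.
- A fresh baseline corrects the starting level, not the change that follows. When the second parent scan serves as the pre scan, the CBT+CCT child has normally met the scanner task before, whereas the CBT-only child has not.
- Parent randomisation makes the arms comparable when they were randomised, not when CBT starts.
- High continuation to CBT limits selection at that step. Joining this study is a further step: 18 are sought from an expected 44 eligible.

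It would also be too strong to say that the plan ignores the RMT period. Sections 9.3.1 and 9.3.4 already provide descriptive statistics and listings by time point. What is missing is a summary of change over that period.

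**Conclusion.** The point stands as one of identification. With the plan followed exactly, the Aim 1 to 3 tests compare RMT followed by CBT+CCT with CBT as first study treatment, and a difference cannot be credited to CCT alone. This rests on the enrolment rules in Sections 4.1, 5.1 and 6.3. If the Section 5.5 clause did admit children from outside the parent study, the overlap would be nearly complete instead of exact, and no planned analysis would exploit the difference.

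A reader might infer three further things that the documents do not support:

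- **That the bias is large, or that it favours CCT.** Nothing in the documents gives its size or sign. It could be zero, could mimic a benefit or could hide one. The rejection rates above rest on assumed shifts.
- **That prior RMT is the only aliased factor.** Completer and opt-in selection and treatment order coincide with CCT just as exactly.
- **That every group difference is inseparable from CCT.** Numbers of tests and scans and the pre-to-post interval differ in pattern but can be described. On the interval, both groups share a floor ("For both groups, participants will have to complete at least 8 intervention sessions") and a common allowance ("participants will be allowed to miss up to 4 sessions of therapy, and the sessions must be completed within 16 weeks"), so the possible ranges overlap.

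The correction should be made before the effect sizes are used, because the next application would otherwise carry them under the wrong name.

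**What to change.** 1. In Sections 4.2, 9.1 and 9.3, state the Aim 1 to 3 contrast as *RMT followed by CBT+CCT versus CBT as first study treatment*. Do not attribute the interaction to CCT alone, and attach this label to any effect size carried into the R01 or R61/R33 application. Cost: text only.
2. For PARS and responder status, add a sensitivity analysis of CBT+CCT against RMT completers who took optional CBT without CCT, if the parent study holds their pre- and post-CBT data. This needs confirming. Section 8.2 suggests that it does, while Section 4.1 lists clinical assessments around this CBT course among what the present study may add. The documents define no responder rule, so one must be written down first. Cost: one analysis. Limits: concurrent comparators are likely to be decliners, since Section 6.3 seeks every possible RMT participant, and earlier ones are non-concurrent. It cannot serve the primary fMRI endpoint, because optional CBT carried no additional scans. For that endpoint, item 1 is the essential correction.
3. Beyond the descriptives and listings already planned, report the RMT-period change in the CBT+CCT arm. Report by group the number of prior tests and scans and the pre-to-post interval. State that this does not identify how RMT alters later CBT response. Cost: one table, largely from data already collected.
4. Reconcile the scan-payment clause in Section 5.5 with inclusion criterion 2 in Section 5.1. Cost: text only.

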4.2 SCIENTIFIC RATIONALE FOR STUDY DESIGN

We hypothesize that CCT, delivered immediately prior to CBT sessions, will exercise task-control network and thereby facilitate the receipt of CBT. So in the control group, age- and gender-matched anxious youth received CBT only; their behavioral, brain and clinical data will serve as comparison, to evaluate whether CCT will augment the CBT effect.

The aims of this project are to:

- (1) Examine whether CBT+CCT will further engage the TCN. We hypothesize that (a) both groups will have increased activation and functional connectivity in task-control network after therapy vs. before therapy; however, (b) the increase will be greater in CBT+CCT vs. CBT only group.
- (2) Examine whether CBT+CCT will further improve cognitive control capacity. We hypothesize that (a) both groups will have improved behavioral performance on the conflict interference task and tasks testing cognitive control capacity included in the NIH Toolbox; however, (b) these effects will be greater in CBT+CCT vs. CBT group.
- (3) Examine whether CCT will augment the CBT outcome. We hypothesize that relative to CBT group, anxiety severity will be reduced more and treatment response rate will be higher in CBT+CCT group.
- (4) Explore the associations between changes in TCN, behavioral and CBT outcome. We hypothesize that increased TCN activation and functional connectivity, and improved behavioral performance on cognitive control tests will correlate with better treatment outcome in both groups.

